9.1. Adverse Events

An adverse event (AE) is defined as any untoward medical occurrence in a subject enrolled into this study regardless of its causal relationship to study treatment. Subjects will be instructed to contact the investigator at any time after randomization if any symptoms develop.

AE analysis tables, namely overall AE tables and summary of all AE events tables, will be summarized. One listing of AE information will be presented, including treatment emergent and non-treatment emergent AEs.

For AEs with missing date, please refer to Table 1 for imputation rules.

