6.1.4. Physical Examination

A complete physical examination will be performed at Screening (Visit 1, Day 1) for eligibility. It will include examination of general appearance, skin, neck (including thyroid), eyes, ears, nose, throat, lungs, heart, abdomen, back, lymph nodes, and extremities, vascular and neurological.

Information for all physical examination findings must be included in the source documentation at the study sites.

Any significant new findings made after signing informed consent form which meet the definition of an AE must be recorded on the Adverse Event CRF page. Refer Section 7.1 for information on definition of adverse event and serious adverse event.

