7.2. Recording Adverse Events and Serious Adverse Events

Recording of adverse events and serious adverse events:

- The Investigator or site staff will be responsible for detecting, documenting and reporting events that meet the definition of an AE or SAE. The Investigator or site staff will then record all relevant information regarding an AE/SAE in the CRF.
- There may be instances when copies of medical records for certain cases are requested by GSK. In this instance, all subject identifiers, with the exception of the subject number, will be blinded on the copies of the medical records prior to submission to GSK.
- The Investigator will attempt to establish a diagnosis of the event based on signs, symptoms, and/or other clinical information. In such cases, the diagnosis will be documented as the AE/SAE and not the individual signs/symptoms. Clinical AEs will be described by diagnosis and not by symptoms when possible (e.g., upper respiratory tract infection, seasonal allergy, etc. instead of runny nose).
- AEs will be collected from the start of the investigational product and until 5 days following last administration of the study product.
- SAEs will be collected over the same time period as stated above for AEs. However, any SAEs assessed as related to study participation (e.g., investigational product, protocol mandated procedures, invasive tests, or change in existing therapy) or related to a GSK concomitant medication will be recorded from the time a subject consents to participate in the study up to and including any follow-up contact.
- Medical conditions reported prior to the time period for reporting AEs/SAEs should be recorded as part of the subject's medical history.

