7.1. Prior and Concomitant Medications

Details of any relevant medical or surgical history, including allergies or drug sensitivity, will be recorded in the CRF. Wherever possible, diagnoses and not symptoms will be recorded. Any medication and non-drug therapies/procedures therapy taken in the 90 days

prior to the Screening Visit will also be recorded. Relevant history will be recorded in the CRF.

For purposes of analysis, prior medications are defined as any medication with a stop date that is prior to the initial study drug dosing date and concomitant medications are defined as any medications with a start date on or after the initial study drug dosing date, but prior to the last study drug dosing or any medications with a start date prior to the initial study drug dosing date and a stop date after the initial study dosing date.

For medications with partial start or stop dates, the partial dates will be imputed according to Table 1 and then will be categorized as prior medication or concomitant medication according to the definitions. Medications with completely missing dates will be included in the concomitant medication summary.

Imputation rules for the start or stop date of missing or incomplete medications are presented in Table 1.

Any changes in concomitant medication or non-drug treatments/procedures will be recorded in subject's e-diary and will also be captured in the CRF. There will be a specific question in the e-diary asking about acetaminophen/paracetamol and all other concomitant medication usage prior to each dose of study treatment.

The number and percentage of subjects receiving prior and concomitant medications will be displayed by medication classes (levels 1 and 2) of the Anatomical Therapeutic Chemical (ATC) classification system and by treatment group using Safety set. A listing of all medications taken by subjects, including those are only prior, will be produced.

Table 1. Imputation rules for the start or stop date of missing or incomplete medications

	Missing	Imputation	Exception
Start date (concomitant medication)	Day	01	Default to Study Day 1 if an event starts the same year and month as Day 1 and the stop date contains a full date and the stop date is later than Day 1; Otherwise If the stop date is prior to Day 1, default to 1 day prior to the stop date

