	Day/Month	01Jan	Default to Study Day 1 if an event started the same year as Day1 and the stop date contains a full date and the stop date is later than Day 1; Otherwise If the stop date is prior to Day 1, default to 1 day prior to the stop date
	Day/Month/Year	No imputation	Assume start prior to study entry.
Stop date (concomitant medication)	Day	Last day of the month	Default to the End of Study Date if the concomitant medication stopped the same year and month as the End of Study Date.
	Day/Month	31DEC	Default to the End of Study Date if the concomitant medication stopped the same year as the End of Study Date.
	Day/Month/Year	No imputation	Assume stops after study end.

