9.1.1. Incidence of Adverse Events

Treatment-emergent adverse events (TEAE) , i.e. AEs that start or worsen during the treatment period (on or after first study medication administration), will be summarized by presenting the number and percentage of subjects having any AE, any AE in each MedDRA System Organ Class (SOC) and having each individual AE (using MedDRA preferred term (PT)). At each level of subject summarization, a subject is counted once if the subject reported one or more events. Percentages will be calculated out of the number of subjects in the Safety population. The number of events will also be presented in the table.

The summary of TEAEs will be presented in descending order from the SOC with the highest total incidence (that is, summed across all treatment groups) to the SOC with the lowest total incidence. If the total incidence for any two or more SOC is equal, the SOC will be presented in alphabetical order. Within each SOC, the PTs will be presented in descending order, in the same manner as SOC.

The incidence of TEAE between treatment groups is compared using a frequency table for Safety population.

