9.1.2. Relationship of Adverse Events to Study Treatment

Summaries of TEAEs which are related to study treatment will be presented by number of subjects. The investigator will provide an assessment of the relationship of the event to the study treatment. A treatment related AE is an event that is related to study medication assessed “Possible” or “Probable” or “Definite” to the question of “Relationship to the study treatment” as reported on an AE CRF page for any subject who had taken one dose of the study medication. TEAEs that are missing a relationship will be presented in the

summary table as “Related” but will be presented in the data listing with a missing relationship. Percentages will be calculated based on the number of subjects in the Safety population.

The TEAE data will be categorized and presented by SOC and PT in a manner similar to that described in Section 9.1.1.

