- g. Nasal swab sample will be obtained from each subject after randomization and self-assessment of common cold symptoms mentioned above for possible future virological analysis.
- h. Independent site personnel, who will have no other responsibilities during the study, will then instruct subjects on proper use, priming and administration technique of study treatment. Subjects will be instructed to dose for the full seven days irrespective of symptom resolution to avoid inappropriate discontinuation due to misinterpretation of reduced symptomatology as a result of the fluctuation of symptoms that occurs with a common cold. Subjects will also be instructed to change to a new study treatment device every 2 days and to prime the new device prior to the morning dose.
- i. Dosing administration is 3 actuations per nostril per dose, four times a day for 7 days. Subjects will be instructed to alternate nostrils after each actuation. First administration of study treatment will occur at the study site by independent site personnel supervision that will have no other responsibilities during the study; first dosing can occur any time prior to 13:00. Subject randomization will be stratified by dosing time on Day 1 by those study subjects receiving first dose of study treatment between the hours of 8:00-11:00 and those receiving first dose of study treatment between the hours 11:01-13:00. On Day 1, subjects dosing between 8:00-11:00 will dose every 4 hours \pm 30 minutes for 4 doses and subjects dosing between 11:01-13:00 will dose every 4 hours \pm 30 minutes for 3 doses. On Days 2-7 all subjects will administer their initial morning dose immediately following recording of their common cold symptom assessment at 07:00 \pm 2 hours and the remaining 3 doses every 4 hours \pm 30 minutes. Dosing times and number of actuations will be recorded in subject's e-diary.
- j. Any serious adverse event assessed as related to study participation that occurs subsequent to the signing of informed consent and any adverse event that occurs subsequent to the first dose will be recorded.
- k. Study conclusion will occur at the Investigator's discretion once all study procedures are complete.

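### SAP 9.1 dates adverse events with the medication table, so undated AEs, and most partly dated AEs with no full stop date after Day 1, drop out of the TEAE tables

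*SAP*

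**What the plan says.** SAP 9.1 has a single instruction for incomplete AE dates: "For AEs with missing date, please refer to Table 1 for imputation rules". Table 1 stands in SAP 7.1, and its title and row labels refer to medications. Its start-date rows work as follows:

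- **Start fully missing:** no date is imputed, and the reader is told "Assume start prior to study entry".
- **Day missing:** the 1st of the month is used. Day 1 replaces it only "if an event starts the same year and month as Day 1 and the stop date contains a full date", and only if that stop date is later than Day 1. If the stop date precedes Day 1, the start is set to the day before the stop.
- **Day and month missing:** 1 January is used, with the same exceptions applied to the year.

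SAP 9.1.1 defines treatment-emergent events as "AEs that start or worsen during the treatment period (on or after first study medication administration"). The incidence tables in 9.1.1 and the related-event tables in 9.1.2 count only these events.

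On collection, Protocol 7.2 states: "AEs will be collected from the start of the investigational product and until 5 days following last administration of the study product". Footnote j in SAP Appendix A agrees: "any adverse event that occurs subsequent to the first dose will be recorded". There are two exceptions. SAEs related to study participation are recorded from consent, and Protocol 6.1.4 says of the screening examination: "Any significant new findings made after signing informed consent form which meet the definition of an AE must be recorded" on the AE page.

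**The concern.** The default suits medications and runs the wrong way for AEs. A medication with an unknown start was often already in use. A non-serious AE on this trial's CRF usually began after first dose, because that is when collection starts. Table 1 nevertheless presumes a pre-dose start, and 9.1.1 then removes the event unless worsening is recorded.

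Two comparisons within the SAP suggest that this was not intended. Section 7.1 keeps medications with no dates at all in the concomitant summary, but nothing equivalent is written for AEs. The other missing AE fields take the cautious value: 9.1.3 counts missing severity as severe, and the sentence in 9.1.2 that opens "TEAEs that are missing a relationship will be presented in the" places such events in the related category. That second default covers only TEAEs, so an undated AE never reaches it.

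AEs are the trial's safety endpoint. Protocol 9.2.4 assesses safety by comparing AE incidence between arms, and the SAP makes that comparison in the TEAE table.

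**Working it through.** The documents state no figure on this point, so the check applies Table 1 to events that truly began after first dose and counts how often the imputed start falls before Day 1.

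**Example.** Day 1 is 18 January, and an AE is recorded as starting on an unknown day in January. If it is ongoing, Table 1 gives 1 January and it is not a TEAE. If it stopped on 25 January, Table 1 gives 18 January and it is a TEAE. The unresolved event is the one lost.

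**Inputs and assumptions.** Day 1 is equally likely to be any of the 1461 dates in a four-year cycle (48 months). Onset is *k* days after Day 1, with *k* = 0 to *W* − 1 equally likely. Three windows are used: *W* = 1 (onset on Day 1), *W* = 8 (to the Day 8 visit) and *W* = 12 (last dose on Day 7, plus the 5 days in Protocol 7.2). No full stop date after Day 1 exists.

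**Day missing.** The imputed start is the 1st of the onset month. It precedes Day 1 when onset falls in the same month as Day 1 and Day 1 is not itself the 1st. In a month of *L* days that holds for *L* − 1 − *k* dates. Over 48 months the count is 1461 − 48 − 48*k* = 1413 − 48*k*. The mean of *k* is (*W* − 1)/2, so the share lost is [1413 − 24(*W* − 1)] / 1461.

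**Day and month missing.** The imputed start is 1 January of the onset year. The same argument over 4 years gives [1457 − 2(*W* − 1)] / 1461.

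| Onset window | Day missing | Day and month missing |
|---|---|---|
| Day 1 only | 1413/1461 = 96.7% | 1457/1461 = 99.7% |
| Days 1–8 | 1245/1461 = 85.2% | 1443/1461 = 98.8% |
| Days 1–12 | 1149/1461 = 78.6% | 1435/1461 = 98.2% |

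The Day 1 row also covers an AE that stopped on Day 1: its stop date is neither before nor after Day 1, so neither exception applies. The longer windows lose fewer day-missing events because an onset in the next month is set to the 1st of that month, which is after Day 1. Where the recorded month is the month of Day 1, the loss over Days 1–12 is 1149/(1461 − 24 × 11) = 1149/1197 = 96.0%.

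**Start fully missing.** All are presumed to precede study entry: 100%.

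**Full stop date after Day 1.** A start in the Day 1 month or year becomes Day 1, and a later one becomes the first day of its own month or year: 0% lost.

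**Weight of one event.** With 85 subjects per arm, one lost subject is 1/85 = 1.2 percentage points.

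**The case against.** The literal reading of the SAP is not in dispute. The case for treating this as a minor clarification has five parts.

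- **Few events are likely.** Treatment lasts 7 days, AEs go into an e-diary, sites ask a standard AE question at each visit, and edit checks and monitoring follow. An unknown month or year for an onset in the past week is implausible, as is an unknown start day for an AE that stopped on Day 1. This stands: the percentages apply only to AEs that already lack date parts.
- **Other tables may keep the events.** SAP 9.1 mentions overall AE tables and a summary of all AEs, and the severity table in 9.1.3 is not worded as TEAE-only. The point is ambiguous, since the all-AE tables are undefined and Protocol 9.3.4 limits the severity table to TEAEs. Either way, the TEAE and related-TEAE counts are not restored.
- **One lost AE need not remove a subject.** Subjects are counted once per row, so 1.2 points is the most that one lost event can change a row. This stands.
- **No bias between arms is shown.** The rule ignores treatment, recording is blinded, and the comparison is a descriptive frequency table. This stands too; the harm is understated incidence, not a demonstrated tilt.
- **A programmer might read 7.1 generously**, either by counting an imputed stop date as a full date or by extending the medication safeguard to AEs. The first reading would rescue some AEs with a partial stop date, but none without a stop date. The second is not written for AEs.

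**Conclusion.** The rule as written gives the wrong result. Truly post-dose, non-serious AEs leave the TEAE and related-TEAE tables always when the start is fully missing. Of those that are ongoing, about 79–85% leave when the day is missing and about 98–99% when day and month are missing. These shares assume evenly spread Day 1 dates and onsets, a full date taken to mean a recorded one, and no recorded worsening after first dose.

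The consequence is limited. The number of affected AEs cannot be known from the documents and may be small, all AEs remain in the listing, and SAP 9.1.4 summarizes SAEs whatever their treatment-emergent status. It should still be corrected before unblinding, because it affects the main safety comparison and is easily put right.

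**What to change.** Keep Table 1's stop-date rows for AEs. In SAP 9.1, replace the reference to its start-date rows with:

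> If an AE start date is fully missing, or its known parts are compatible with the first-dose date, it is set to the first-dose date. If the known month or year is after that of first dose, the first day of that month or year is used. The AE counts as treatment-emergent unless the known start parts or the stop date show that it began or ended before first dose; in that case Table 1 as printed in Section 7.1 applies.

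The third sentence overrides the first, so an undated AE that stopped before first dose stays out of the TEAE tables. Under this rule none of the truly post-dose events described above is lost.

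The cost is three sentences and no new data. TEAE counts may rise slightly and could include an undated pre-dose finding entered on the AE page. That errs in the same direction as the SAP's defaults for missing severity and relationship.

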9.1.1. Incidence of Adverse Events

Treatment-emergent adverse events (TEAE) , i.e. AEs that start or worsen during the treatment period (on or after first study medication administration), will be summarized by presenting the number and percentage of subjects having any AE, any AE in each MedDRA System Organ Class (SOC) and having each individual AE (using MedDRA preferred term (PT)). At each level of subject summarization, a subject is counted once if the subject reported one or more events. Percentages will be calculated out of the number of subjects in the Safety population. The number of events will also be presented in the table.

The summary of TEAEs will be presented in descending order from the SOC with the highest total incidence (that is, summed across all treatment groups) to the SOC with the lowest total incidence. If the total incidence for any two or more SOC is equal, the SOC will be presented in alphabetical order. Within each SOC, the PTs will be presented in descending order, in the same manner as SOC.

The incidence of TEAE between treatment groups is compared using a frequency table for Safety population.

9.1.2. Relationship of Adverse Events to Study Treatment

Summaries of TEAEs which are related to study treatment will be presented by number of subjects. The investigator will provide an assessment of the relationship of the event to the study treatment. A treatment related AE is an event that is related to study medication assessed “Possible” or “Probable” or “Definite” to the question of “Relationship to the study treatment” as reported on an AE CRF page for any subject who had taken one dose of the study medication. TEAEs that are missing a relationship will be presented in the

summary table as “Related” but will be presented in the data listing with a missing relationship. Percentages will be calculated based on the number of subjects in the Safety population.

The TEAE data will be categorized and presented by SOC and PT in a manner similar to that described in Section 9.1.1.

9.1.3. Severity of Adverse Event

A summary of AEs by treatment and severity will be presented in a table. In the AE severity table, if a subject reported multiple occurrences of the same AE, only the most severe AE will be presented. AEs with missing severity will be included in the summary table as severe, but will be presented in the data listing with a missing severity. Percentages will be calculated out of the number of subjects in the Safety population.

9.1.4. Serious Adverse Events

A SAE is defined as any untoward medical occurrence that at any dose results in death, is life-threatening, requires inpatient hospitalization or prolongation, results in significant disability/incapacity, is a congenital anomaly/birth defect, is an important medical events that may jeopardize the subject or may require medical intervention to prevent one of the outcomes listed above. SAEs will be collected through the end of the study.

All SAEs, regardless of their treatment-emergent status will be summarized by system organ class (SOC) and PT. Percentages will be calculated out of the number of subjects in the Safety population.

All SAEs will be presented in a listing.

9.1.5. Adverse Events Leading to Study Discontinuation

All subjects who have an AE where the answer to “Did the subject withdraw from study as a result of AE?” is “Yes” will be presented in a listing.

9.1.6. Death

All deaths will be presented in a listing.

9.2. Clinical Laboratory Evaluations

9.2.1. Urine Drug Screen and Pregnancy Test

Urine will be collected at screening to perform urine drug test (urine dipstick). Urine will be tested for the following drugs or illicit substances: barbiturates, benzodiazepines, amphetamines, cocaine, opiates, and cannabis. In case of a positive finding at the screening visits or any substance class, the subject must be excluded from participation in the study. Results will be recorded in the CRF.

All women of childbearing potential will have a urine pregnancy test. It will be conducted at the site using a urine dipstick. A positive urine pregnancy test disqualifies a subject from the study. Results from the pregnancy test will be recorded in the CRF.

Number of subjects in each substance will be summarized and all laboratory data will be presented in a listing. Urine drug and pregnancy test for women will also be presented in listings.

9.3. Vital Sign Measurements

Vital sign data will be collected, including

- sitting systolic blood pressure (mmHg) which is the average of 3 measurements,
- sitting diastolic blood pressure (mmHg) which is the average of 3 measurements,
- pulse rate (beats per minute),
- respiration rate (breath per min),
- oral body temperature (°C)
- height (cm)
- weight (kg)

Summary table for change from baseline will be presented for the collected data by treatment group for subjects in the Safety population. Baseline height and weight will be summarized with other demographic parameters.

All vital sign data by subject will also be presented in a listing.

9.4. Physical Examination

A complete physical examination will be performed at Screening (Visit 1, Day 1) for eligibility. It will include examination of general appearance, skin, neck (including thyroid), eyes, ears, nose, throat, lungs, heart, abdomen, back, lymph nodes, and extremities, vascular and neurological.

All physical examination by subject in the Safety population will be presented in a listing.

